4.2 Placebos and study drug packaging

Tamoxifen and placebo tablets will be overencapsulated by the Investigational Drug Pharmacy at Vanderbilt University Medical Center. At the Investigational Drug Pharmacy, capsules will be packaged into HDPE bottles with a liner, cotton, and childproof cap. Bottles will be fully labeled to meet state and FDA requirements, and packaged into labeled kits. There will be one bottle of drug product dispensed to study subjects at the baseline study visit and at the 12 week visit during the treatment phase. Study drug must be stored at room temperature and protected from moisture. Subjects will be asked to bring bottles at the 12 week and 24 week study visits to allow for tracking of adherence and medication control. At the end of the study, after accountability has been completed, study product will be destroyed at the Investigational Drug Pharmacy.

4.4 Management of other medical therapies during the trial

Subjects with PAH are often treated with a combination of medicinal therapies. Those include diuretics, digoxin, phosphodiesterase-5 inhibitors, endothelin receptor antagonists, calcium channel blockers, soluble guanylate cyclase activators, and prostacyclin or prostacyclin analogues or prostacyclin receptor agonists. Withholding therapy which is the current standard of care is unethical in PAH, considering the high risk of morbidity and mortality. In addition, new drugs should add incremental benefit to established therapies to really improve outcomes. The subjects' pre-study medical regimen will therefore be continued after enrollment in the study. There will be no constraints on the management of the subjects' PAH medications during the study period.

As noted above, Bosentan, an agent used in the treatment of PAH, is an inducer of CYP3A4. While there are no studies of the interaction of tamoxifen and bosentan, bosentan may reduce the concentration of tamoxifen.

Excluded concomitant therapy:

- Bosentan
- Selexipag
- Hormone therapy (including estrogen, progesterone, testosterone, DHEA), other selective estrogen receptor modulators, and aromatase inhibitors.

4.5 Treatment masking

All study personnel and subjects will be masked for the duration of the study until the last subject completes follow-up assessments. The VUMC Investigational Drug Pharmacist, the unblinded statistical analyst, and the DSMB will be unmasked; the Investigational Drug Pharmacist will supply the DSMB and the identified biostatistician with the drug/placebo identifier. This review will occur only in a closed meeting.

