3.4 Maintenance of treatment randomization code and procedures for breaking the code

The treatment randomization code will be maintained by the research pharmacist at Vanderbilt University Medical Center. The code is to be broken only if knowledge of treatment assignment for that subject is required to initiate appropriate therapy of an adverse event (AE) or if the safety of the subject is at serious risk if treatment is continued without knowledge of the treatment assignment. The decision to unmask will be made by the PI ([name]), [name], and the Chair (or co-Chair) of the Data Safety Monitoring Board.

Unblinding may only occur for emergency purposes which would affect clinical care. Investigators should note that the occurrence of a serious adverse event or progressive disease should not routinely precipitate the immediate unblinding of the label. Even with unblinding, the number of unblinded individuals should be limited to only those who need to know the treatment identity (e.g., only the local physician caring for the subject).

Chapter 4. Treatments

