5.1.2 Study Day – Visit 1 (Baseline)

Informed consent will occur at the time of the baseline visit.

The research coordinator will call the subject 1-2 days before the visit as a reminder. The coordinator will instruct the subject to not eat or drink (except water) and to avoid heavy exercise for 12 hours before the study day assessment. Subjects will be instructed to take their routine medications on the morning of the visit and to bring their

medications and a snack or meal with them to the visit to take at the center after blood draw.

Baseline information will be used to characterize the participants and to compare the experimental groups with regards to demographics and other variables. Eligibility criteria will be confirmed prior to randomization to treatment group.

The subject will arrive at the study site outpatient clinic or clinical research center. The following procedures will be performed:

- Phlebotomy
- Urine collection
- Electrocardiogram
- Echocardiography
- Eat a small snack
- Interim medical history
- Review current medications
- WHO functional class assessment
- Vital signs
- Physical exam
- Review of inclusion/exclusion criteria
- ESR-specific PET study
- Complete SF-36 and emPHasis-10 forms
- Six minute walk test
- Randomization to treatment group
- Provide diary and instructions
- Dispense supply of study drug
- Reinforce instructions on recording of new medications and dose changes
- Reinforce instructions on bringing the subject's routine and study medications to all visits
- Reinforce counseling regarding birth control with premenopausal female subjects

Fasting serumpregnancy test will be performed. Fasting urine sample and fasting blood samples for study assays will be processed and banked. Echocardiography will be performed. After the electrocardiogram and echocardiogram, the subject will have the opportunity to eat a snack. The investigator or research nurse will take a history/interim history, check vital signs, and review current medications. A physician will perform a physical examination and review current medications. ESR-specific PET study will be conducted. The subject will complete the SF36 and emPHasis-10. The subject will then perform a six minute walk test (6MWT).

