5.1.6 Study Day – Visit 3 (Week 24 ± 3 days)

The research coordinator will call the subject 1-2 days before the visit as a reminder. The coordinator will instruct the subject to not eat or drink (except water) and to avoid heavy exercise for 12 hours before the study day assessment. Subjects will be instructed to take their routine medications on the morning of the visit and to bring their medications and a snack or meal with them to the visit to take at the center after blood draw.

The subject will arrive at the study site outpatient clinic or clinical research center. The following procedures will be performed:

- Phlebotomy
- Urine collection
- Electrocardiogram
- Echocardiography
- Eat a small snack
- Interim medical history
- Review current medications
- WHO functional class assessment
- Vital signs
- Physical exam
- ESR-specific PET study
- Complete SF-36 and emPHasis-10 forms
- Six minute walk test
- Review study drug compliance
- Turn in study diary and any remaining study medication

Fasting urine sample and blood samples for study assays will be processed and banked. Echocardiography will be performed. After the echocardiogram, the subject will have the opportunity to eat a snack. The investigator or research nurse will take a history/interim history and perform a physical examination including checking vital signs, and review current medications. ESR-specific PET study will be conducted. The subject will complete the SF36 and emPHasis-10. The subject will then perform a six minute walk test (6MWT).

Once all procedures are complete the research coordinator will thank the subject for his/her attendance and study participation. The subject's primary PAH physician and medical doctor will be alerted to the subject's completed participation in the clinical trial.

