5.1.7 Telephone follow-up (Week 25)

The research coordinator will call the subject approximately 1 week after the Week 24 visit. Symptoms and potential ongoing side effects after stopping study drug will be assessed. Serious adverse events will continue to be followed until resolution. The research coordinator will once again thank the subject for participation in the study.

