7.3 Statistical procedures

7.3.1 Data analysis

The intent-to-treat analysis will include all randomized subjects. Hypothesis testing will use two-sided $\alpha = 0.05$ without correction for multiplicity.

The primary and secondary endpoints are described in Chapter 6.

Continuous endpoints will be analyzed using the Wilcoxon Rank Sum test to assess between treatment arms difference and using the signed rank test for within-group change from baseline. For binary endpoints, Fischer's exact test will be used to assess between treatment arms difference.

For the primary endpoint, TAPSE, an exploratory analysis using mixed effects model will be conducted to assess the time trend and treatment effect (tamoxifen vs placebo). The mixed effects models will have a random subject effect and we will use an autoregressive model of order 1 (AR1) or other plausible covariance structures for the error covariance. In addition, the association between baseline (pre-tamoxifen or placebo) lung ESR density and response to treatment quantified by TAPSE and 6MWT distance will also be evaluated using the mixed effects models. These analyses will be of particular interest since they will help us *a priori* to identify patients who will be most likely responders to tamoxifen in the next-phase studies should this proof-of-concept study be a success.

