8.2 Data quality

The lead investigators, Drs. [name] and/or [name], will perform continuous monitoring of data quality and completion of CRFs.

Periodic audits will be conducted. The research staff will review database forms and source documents to ensure that the information on the forms is complete and consistent with the source documents. All consent forms and screening logs will be audited.

Chapter 9. Participant Safety and Confidentiality

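### Section 4.5 lets masking of study personnel end at the last subject's follow-up rather than at database lock, so any reads, assays or queries still open could be finished with the arms known

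*Combined protocol and SAP*

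**What the plan says.** Section 4.5 gives the only general rule on when masking ends: "All study personnel and subjects will be masked for the duration of the study until the last subject completes follow-up assessments". The next sentence names the exceptions during the trial: "The VUMC Investigational Drug Pharmacist, the unblinded statistical analyst, and the DSMB will be unmasked". The last scheduled contact is the Week 25 call in section 5.1.7: "The research coordinator will call the subject approximately 1 week after the Week 24 visit".

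Section 3.4 leaves the randomization code with the research pharmacist and adds: "Unblinding may only occur for emergency purposes which would affect clinical care". That governs code breaks for individual subjects. It sets no later end point for the trial as a whole.

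On work that could still be open at that time:

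- **Samples.** Section 5.1.2 says of baseline "Fasting urine sample and fasting blood samples for study assays will be processed and banked", and section 5.1.6 says of Week 24 "Fasting urine sample and blood samples for study assays will be processed and banked". Neither gives an assay date or a masking rule for the laboratory.
- **Imaging.** Sections 5.1.2, 5.1.4 and 5.1.6 have echocardiography done at each visit and PET at baseline and Week 24. They do not say who reads the images, when, or whether the reader is masked.
- **Data.** Section 8.2 says "The research staff will review database forms and source documents" to check completeness and consistency. The introduction to Chapter 8 places data queries across the trial. Neither states a cut-off or a lock.
- **Adverse events.** Section 9.4.6 has unresolved events followed until they resolve, are explained, or the subject is lost.

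**The concern.** Masking protects a result up to the point where the data can no longer change, and that point is normally database lock. The last subject's last contact comes earlier. In between, samples may be assayed, images finalised or re-measured, queries answered and open adverse events followed. If staff may know the arms by then, those steps lose their protection.

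The primary endpoint, change in TAPSE, is measured from echo images, and there are only 12 patients per arm. The standard error of a between-arm difference is 0.25 × √(2/12) = 0.10 cm, so a systematic reading difference of that size would be a full standard error. The hormone and biomarker aims depend on the banked samples.

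**Working it through.** **Step 1: the passages side by side.** Section 4.5 is the only general end point, and it falls at the last follow-up assessment. Section 3.4 covers emergencies only. The document nowhere makes database lock, completed reads, completed assays or closed queries a condition for unmasking. Sections 5.1.2 and 5.1.6 bank samples without an assay date, and 9.4.6 expects some adverse events to be still open at the last visit. The text therefore permits such work to be done after unmasking. It does not order it.

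**Step 2: inputs for an illustration.** Section 7.4 gives an SD of the within-subject difference of 0.25 cm and 12 completers per arm. Section 7.3.1 gives a two-sided α of 0.05 and the rank-sum test between arms. The size of a reading bias is *not* in the document. I take 0.10 cm, half of the 0.20 cm drop in section 7.4, as an assumption.

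**Step 3: the plan's own figure.** With a paired t-test in one arm, n = 12 and 11 df, the noncentrality is d/SD × √n.

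- d = 0.20: 0.20/0.25 × √12 = 2.77, power 71.4% (plan: 71%).
- d = 0.25: 0.25/0.25 × √12 = 3.46, power 88.3% (plan: 88%).

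The stated power is thus reproduced with 0.25 cm as the SD of a patient's change. That is how it is used below. The present point does not dispute the power figure, and the fix does not alter it.

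**Step 4: bias in every patient of one arm.** There is no true effect. Changes are drawn from N(b, 0.25) in one arm and N(0, 0.25) in the other, 12 per arm, and tested with the exact two-sided rank-sum test. The test rejects at U ≤ 37 or U ≥ 107, so its exact size is 4.5%. Simulated rejection rates:

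| Bias b in all 12 patients | Rejection rate |
|---|---|
| 0 | about 4.5% |
| 0.05 cm | about 7% |
| 0.10 cm | about 14% |

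As a cross-check, the two-sample t-test (22 df) has noncentrality b/0.25 × √(12/2). This is 0.49 for 0.05 cm and 0.98 for 0.10 cm, giving 7.6% and 15.5%.

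**Step 5: bias in only some patients.** The 0.10 cm bias is now applied to k of the 12 patients in one arm.

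| Patients affected (k) | Mean shift 0.10 × k/12 | Rejection rate |
|---|---|---|
| 1 | 0.008 cm | about 4.5% |
| 3 | 0.025 cm | about 5% |
| 6 | 0.050 cm | about 6.5% |
| 12 | 0.100 cm | about 14% |

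Which row is relevant depends on how many TAPSE values are still open when the arms become known. The document does not say. Section 3.1.1 plans pre-screening over 4 years. If echoes are read soon after each visit, only the last few would be open; if they are read in one batch at the end, all would be.

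**The case against.** The strongest reply is that section 4.5 sets a minimum duration and does not direct unmasking on that day. The pharmacist holds the code (3.4), and no passage orders its release at the last follow-up. Section 9.5 puts a study code number on forms, records and blood samples, so a tube does not show the arm. All echo and PET images, walk tests and questionnaires are acquired while staff and subjects are masked. A manual of procedures is mentioned in section 8.1 but was not available for this review; it may contain rules on reading and lock.

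Most of this stands, and it limits the weight of the point. It does not close the gap. Code numbers protect little once staff who can link number to subject may also know the arm, and section 9.5 gives project staff access to that list. If the manual sets a later end point, 4.5 should agree with it.

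A reader might infer more than the document supports:

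- *That late reads will be made unmasked, or that the false-positive rate is 14%.* No passage says TAPSE is read or re-read after the last follow-up. The 14% needs both an assumed bias and its presence in every patient of an arm.
- *That open model choices expose the primary result.* Section 7.3.1 fixes the rank-sum test between arms. The wording "we will use an autoregressive model of order 1 (AR1) or other plausible covariance structures for the error covariance" belongs to mixed models; the one for TAPSE is labelled exploratory, and the other relates baseline ESR density to response. The unspecified covariance structure, echo metrics and biomarkers are separate gaps in specification.
- *That queries and attribution of adverse events are known to continue after follow-up.* Chapter 8 places queries over the time of the trial, and 9.4.6 speaks of following unresolved events. Later work of this kind is possible but not stated.
- *That blinding is lost.* Because acquisition is masked, early unmasking would weaken the protection, not remove it.

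**Conclusion.** The point holds as a weakness in the masking rule. Section 4.5 ends the required masking at the last subject's follow-up, and nothing in the document extends it to database lock. Work that can still change the data may then be finished with the arms known.

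Its size cannot be derived from the document. With an SD of 0.25 cm, 12 per arm, no true effect and an assumed 0.10 cm bias, the false-positive rate goes from about 4.5% to about 14% if all patients in an arm are affected. It is about 6.5% or less if half or fewer are. The primary test is fixed and is exposed only through late reads or late data changes, if there are any. This is a cheap improvement, not a fault that invalidates the design.

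**What to change.** In section 4.5, replace the present end point with this condition: masking continues until all echo and PET reads and all study assays are complete, data queries are closed and the database is locked. Keep the emergency exception of section 3.4 and the unmasked roles named in 4.5. If the manual of procedures has rules on reading or lock, make the two agree.

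Sample size, α, power, visits and treatment are unchanged. The cost is a wording change in 4.5 and somewhat later unmasking of staff and subjects. How much later depends on how long reads, assays and cleaning take, which the document does not say.

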4.6 Drug Logistics and Accountability

All study drugs will be stored in accordance with Good Clinical Practice (GCP) and Good Manufacturing Practices (GMP) requirements and the instructions given by the clinical supplies department at Vanderbilt University Medical Center. Study drugs will not be accessible to unauthorized personnel.

4.6.1 Accountability

The lead study investigator at VUMC must maintain a careful record of the inventory and disposition of the investigational agent using the drug accountability form.

4.6.2 Destruction and Return

At the end of the study, unused supplies of tamoxifen should be destroyed according to institutional policies. Destruction will be documented in the drug accountability record.

Chapter 5. Data Collection

5.1 Study Visits and Contacts

5.1.1 Screening Phone Call

Potentially eligible subjects will be identified by pre-screening or if there is expressed interest in enrolling. The subject will be contacted by telephone or in person by the research coordinator. The following procedures will be performed:

- Review of inclusion/exclusion criteria
- Review medical history
- Review current medications
- Determine WHO functional class based upon providers most recent clinic note.
- Provide instructions on participation in the study, including how to record the use of new medication (tamoxifen) administration
- Instruct subjects to bring routine medications to baseline visit, do not eat or drink (except water) 12 hours before baseline visit, and to avoid heavy exercise for 12 hours before the baseline visit

Subjects will be reminded that pregnancy is a known complication in subjects with PAH, with a high risk of heart failure and death (mortality rates exceed 50%) among those PAH patients who proceed with pregnancy⁴⁶. As a result, pregnancy is strongly discouraged in patients with PAH⁴⁷. As a result, effective and safe contraception is of fundamental importance and these aspects are discussed in depth with every woman of childbearing potential diagnosed with PAH in our care program at Vanderbilt University Medical Center. In addition, several of the medications used for PAH (e.g., bosentan) are potentially teratogenic and require demonstration of two forms of birth control for their continued use, and monthly monitoring for pregnancy. Thus, the females eligible for this trial should all be on at least two forms of contraception (e.g., IUD plus the use of a barrier contraceptive method) at the time of screening and review for inclusion. However, as part of the informed consent process, this will be reviewed with patients at length. All female subjects of childbearing potential should be on at least two forms of contraception (e.g., non-hormonal IUD plus the use of a barrier contraceptive method).

After the screening phone call, the subject will be scheduled for a baseline study visit within 21 days at the study center.

5.1.2 Study Day – Visit 1 (Baseline)

Informed consent will occur at the time of the baseline visit.

The research coordinator will call the subject 1-2 days before the visit as a reminder. The coordinator will instruct the subject to not eat or drink (except water) and to avoid heavy exercise for 12 hours before the study day assessment. Subjects will be instructed to take their routine medications on the morning of the visit and to bring their

medications and a snack or meal with them to the visit to take at the center after blood draw.

Baseline information will be used to characterize the participants and to compare the experimental groups with regards to demographics and other variables. Eligibility criteria will be confirmed prior to randomization to treatment group.

The subject will arrive at the study site outpatient clinic or clinical research center. The following procedures will be performed:

- Phlebotomy
- Urine collection
- Electrocardiogram
- Echocardiography
- Eat a small snack
- Interim medical history
- Review current medications
- WHO functional class assessment
- Vital signs
- Physical exam
- Review of inclusion/exclusion criteria
- ESR-specific PET study
- Complete SF-36 and emPHasis-10 forms
- Six minute walk test
- Randomization to treatment group
- Provide diary and instructions
- Dispense supply of study drug
- Reinforce instructions on recording of new medications and dose changes
- Reinforce instructions on bringing the subject's routine and study medications to all visits
- Reinforce counseling regarding birth control with premenopausal female subjects

Fasting serumpregnancy test will be performed. Fasting urine sample and fasting blood samples for study assays will be processed and banked. Echocardiography will be performed. After the electrocardiogram and echocardiogram, the subject will have the opportunity to eat a snack. The investigator or research nurse will take a history/interim history, check vital signs, and review current medications. A physician will perform a physical examination and review current medications. ESR-specific PET study will be conducted. The subject will complete the SF36 and emPHasis-10. The subject will then perform a six minute walk test (6MWT).

All inclusion/exclusion criteria confirmed by an investigator before the subject can be formally randomized. The subject will be randomized to a treatment group. A pre-packaged 13 week supply of study medication (tamoxifen 20 mg or placebo) will be given to the subject. The subject will be instructed to take one tablet in the morning once each day with or without food starting **the day after the baseline visit** (i.e., if the baseline visit is on a Tuesday, the subject should start study mediation the next day,

Wednesday). After study drug is dispensed, the research coordinator will provide instructions on how to complete the study drug diary.

Once all procedures are complete and study drug provided, the research coordinator will thank the subject for his/her attendance and reinforce compliance with the study medication and protocol. The subject's primary PAH physician and medical doctor will be alerted to the subject's participation in the clinical trial.

The research coordinator will call the subject on the morning of study day 1 to remind the subject to begin taking the study medication.

5.1.3 Phone Call (Week 1 ± 2 days; Week 3 ± 2 days; Week 6 ± 2 days; Week 9 ± 2 days)

The research coordinator will call the subject. Symptoms and potential side effects will be assessed and changes in medications will be reviewed/recorded. Pregnancy avoidance will be stressed. Medication compliance will be assessed and reinforced. Subject questions will be answered.

